Cover Page

Methylprednisolone Taper to Treat Delayed Post-Operative Recovery After Total Knee Arthroplasty: a Double-Blind Randomized Controlled Trial

Clinical Trials: NCT05113901

IRB: ORA 21080501

Approved: 9/2/21

Methylprednisolone Taper Research Protocol

I. Title:

Methylprednisolone Taper to Treat Delayed Post-Operative Recovery After Total Knee Arthroplasty: a Double-Blind Randomized Controlled Trial

II. Authors:

[name], BS, [name], BA, [name] [name], [name], MSc, [name], and [name]

III. Purpose:

To evaluate the efficacy of a methylprednisolone taper on patients with decreased range of motion (ROM) or delayed recovery in the acute postoperative period following total knee arthroplasty (TKA).

IV. Hypothesis:

Patients with decreased ROM or delayed recovery six weeks to three months post-TKA will improve ROM and patient-reported outcomes at two weeks post-treatment initiation of methylprednisolone taper, as compared to similar patients who receive a placebo taper.

V. Background:

Total knee arthroplasty (TKA) is one of the most performed and efficacious orthopaedic procedures, with an estimated 7 million people living with a total knee prosthesis in 2010. The number of annual TKAs is predicted to increase by 85% by 2030 and 143% by 2050, equating to 1.26 million² and 1.5 million³ procedures per year, respectively. In recent studies, knee prostheses have demonstrated their efficacy in 10-, 20-, and 25-year survival rates of 96.1%, 89.7%⁴, and 82.3%⁵, respectively. Similarly, comparing functional and patient-reported outcomes before and after surgery have confirmed the high success rate achieved with this procedure. However, recovery following total knee arthroplasty (TKA) in the acute postoperative period is variable. Most clinical improvements are achieved within the first three months postoperatively but can continue up to one year. There is currently a paucity of data evaluating the efficacy of oral corticosteroids in the six-week to three-month postoperative period in slowly recovering patients.

Few treatments have been studied for patients who fail to achieve early range of motion or pain reduction milestones in the perioperative period. Periarticular and systemic corticosteroids improve pain and function in the immediate postoperative period, without an increase in adverse events. ¹²⁻¹⁶ Additional doses of corticosteroids administered at 24 and 48 hours postoperatively have demonstrated greater improvements in pain and ROM compared to perioperative administration, with no difference in complication rates. ¹⁷⁻²⁰ However, few studies have evaluated the use of oral corticosteroids within a multimodal pain management regimen. Gardiner et al. evaluated low-dose steroids 10 days immediately following lumbar laminectomy and/or discectomy, in addition to a standard opioid regimen, and reported decreased subjective pain scores. ²¹ Gottshalk et al. reported decreased patient reported pain from postoperative days 4-7 in early published results of a randomized controlled trial investigating administration of a methylprednisolone taper immediately following distal radius repair. ²² Importantly, the current

literature demonstrates low- and short-dose corticosteroids are safe.²³ Intraoperative corticosteroids have been shown to improve pain and function in the acute postoperative period, and additional doses in the immediate postoperative period can potentiate and prolong this beneficiary effect, without increasing adverse events. Therefore, a methylprednisolone taper six weeks post-TKA may benefit patients experiencing decreased ROM or delayed recovery, including residual pain.

Following TKA, care is taken to control pain, swelling, and stiffness, all of which may contribute to delayed recovery. For instance, more than 20% of TKA patients develop postoperative stiffness, ²⁴ known as arthrofibrosis, accounting for an estimated 28% of 90-day hospital readmissions. ²⁵ In treating patients with delayed recovery, corticosteroids are of particular interest because of its potent anti-inflammatory effect, evidenced by its ability to decrease postoperative levels of IL-6 and CRP. ¹⁵ Corticosteroids block prostaglandin synthesis, which is responsible for sensitizing nociceptive pain receptors, and reduce vascular permeability, which causes edema following surgery. ^{26, 27} Therefore, by reducing pain and edema, corticosteroids may allow for more effective physical therapy sessions and more rapid improvement in ROM and recovery following TKA.

To the best of our knowledge, this is the first study to investigate the utility of a methylprednisolone taper six weeks to three months postoperatively following TKA. The authors present a double-blinded, randomized-controlled trial evaluating the role of a methylprednisolone taper on patients with decreased ROM or delayed recovery in the acute postoperative period.

VI. Study Design:

Level I: Prospective, double-blinded, randomized controlled trial

VII. Inclusion Criteria:

- Any patient undergoing primary TKA with a diagnosis of osteoarthritis
- \geq 18 years old
- ROM <90° by 3 weeks postoperatively without improvement to >90° by 6 weeks
- Requiring a 30-pill oxycodone refill
- NSAID allergy
- Thigh circumference discrepancy >2cm between legs from 3 to 6 weeks
- Defense and Veterans Pain Rating Scale (DVPRS) > 5 between 3 and 6 weeks
- Willingness to undergo randomization

VIII. Exclusion Criteria:

- Reported chronic corticosteroid or opiate use
- Suspected or confirmed periprosthetic joint infection
- Revision TKA
- Primary diagnosis other than osteoarthritis, including avascular necrosis, fracture, or post-traumatic arthritis
- American Society of Anesthesiologists (ASA) score ≥ 4
- Reported history of liver or renal disease
- Uncontrolled diabetes

- Immunosuppression
- \leq 18 years old
- Inability to take oral medications
- Unable to provide consent

IX. Demographics:

Age, sex, height, weight, BMI, ASA score, comorbidities, and smoking status will be collected

X: Primary Outcome Measure:

Change in ROM from pre-treatment to 8 and 12 weeks post-operatively

XI: Secondary Outcome Measures:

- 1. Patient Reported Outcome Measures:
 - a. DVPRS and Knee Society Score (KSS) at pre-treatment, and 1 week, 3 weeks, 6 weeks, 12 weeks post-treatment
 - b. Daily Visual Analogue Scale (VAS) pain score on days 1-6 of treatment
 - c. Knee Injury and Osteoarthritis Outcome Score for Joint Replacement (KOOS Jr), Veterans Rand 12-Item Health Survey (VR-12), Single Assessment Numeric Evaluation (SANE), Forgotten Joint Score, and UCLA activity score preoperatively, 6 weeks, and 3 months
- 2. Number of manipulations under anesthesia (MUAs)
- 3. Adverse outcomes including infection, avascular necrosis, and 90-day readmission rates

XII. Patients and Protocols:

Recruitment will include patients of four fellowship-trained orthopaedic surgeons in the Division of Adult Reconstruction at Midwest Orthopedics at Rush. Surgeons will include [name] [name], [name], [name], and [name], and enrollment sites will include Midwest Orthopedics at Rush and affiliated outpatient surgical centers. Patient charts will be used to identify qualifying patients at three weeks postoperatively based on inclusion criteria. If these patients continue to meet inclusion criteria at six weeks postoperatively, they will be approached by the attending surgeon and study staff to consent to participation in the study during their regularly scheduled follow-up appointment.

If patients consent to participation in this double-blinded study, they will be randomized to one of two treatment groups. The experimental group will receive a methylprednisolone taper (21 x 4mg capsules) and the control group will receive a placebo taper (21 sugar capsules). In addition to taking assigned capsules, patients will undergo standard postoperative management, including physical therapy. Patients will qualify for MUA if flexion ROM remains <90° at 8 weeks.

Methylprednisolone and placebo capsules will be stored securely in locked cabinets at the Research Coordinator's desk. At the time of consent, a sealed, numbered envelope will be drawn from a box, and will contain the patient's randomization assignment (i.e. a piece of paper indicating experimental or control group). To maintain blinding, these envelopes will be packaged by study staff, but not the attending surgeon. Assigned capsules, stored in prescription pill bottles, will be administered at the conclusion of the follow-up appointment based upon the randomization assignment within the sealed envelopes. Patients will be provided with paper

instructions regarding how take the medication, including six capsules per os (PO) on day one, five capsules on day two, four on day three, three on day four, two on day five, and one on day six. These instructions will contain a chart detailing how many capsules to take, and at what time to take them (Appendix 1). Day one is defined as day of consent. The methylprednisolone and placebo capsules will be provided by Dermasave Labs, Inc. (Pleasant Valley, NY), a registered compounding pharmacy with the state of New York, operated by a New York licensed pharmacist with 36 years of industry experience.

Patients will be enrolled in STREAMD, a text messaging service that texts prompts to patients. Daily text messages will include reminders with the required number of pills to be taken on the corresponding day of the taper. At the time of consent, knee flexion ROM will be recorded by the attending physician and this information will be extracted from the chart. ROM will then be extracted from patient charts weekly for eight weeks using clinic or physical therapy notes as needed. PROMs collected at the time of consent will include DVPRS and KSS. DVPRS and KSS will also be collected at one week, 3 weeks, 6 weeks, and 12 weeks post-treatment. DVPRS will be administered via STREAMD. Patients will respond directly via text message reply indicating a score. VAS pain score will be collected daily on days 1-6 of the taper, via STREAMD. KSS will be completed via the PatientIQ system, which is currently used for all research related forms. For any patient that cannot use these services, surveys will be administered over the phone. All patients, whether enrolled in studies or not, complete KOOS Jr, VR-12, SANE, Forgotten Joint, and UCLA scores preoperatively, and at six weeks and three months postoperatively.

XIII. Sample Size:

Power analysis used mean flexion of $111.4^{\circ} \pm 16.0^{\circ}$, reported by Bettger et al. at 6 weeks post-TKA.²⁸ Control and treatment groups are assumed to have the same standard deviation. Following precedent, a change in ROM of 10° was defined as clinically important.^{29, 30} At an alpha of 0.05, 112 patients (56 per arm) will provide 90% power to detect a 10° change. Assuming a 20% dropout, 136 patients (68 per arm) will be recruited.

XIV. Treatment Groups:

- 1. Methylprednisolone taper 21 x 4mg tablets at 6 weeks, qualifying for MUA if ROM <90° at 8 weeks
- 2. Placebo taper 21 sugar tablets at 6 weeks with standard management, qualifying for MUA if ROM <90° at 8 weeks

XV. Risks and Benefits:

Most potential risks relate to medication side effects. Side effects can be categorized by organ system and include: dermatologic and appearance (skin thinning, weight gain, acne, hirsutism, alopecia, ecchymoses, Cushingoid appearance, striae), ophthalmologic (cataracts, increased intraocular pressure, exophthalmos), cardiovascular (fluid retention, hypertension, arrythmias, premature atherosclerosis, increased lipid levels), gastrointestinal (peptic ulcer disease, gastritis, gastrointestinal bleeding, steatohepatitis), bone and muscle (avascular necrosis, osteoporosis, myopathy), neuropsychiatric (mood disorders, insomnia, akathisia, psychosis, impaired memory), metabolic and endocrine (hyperglycemia, hypothalamic-pituitary-adrenal axis suppression), immune system (increased infection risk), and hematologic (leukocytosis). 31, 32

However, risk of side effects are proportional to dose and chronicity of treatment, with many of the reported outcomes attributed to rheumatoid arthritis patients on chronic or high dose corticosteroids. ^{33, 34} Importantly, a methylprednisolone taper pack is defined as a low- and short-dose corticosteroid treatment, which is considered safe by the current literature. ²³ A randomized controlled trial evaluating a 15-day oral prednisone taper versus placebo for radiculopathy due to a herniated lumbar disk found an increase in minor adverse events including insomnia, nervousness, increased appetite, indigestion, headache, joint pain, and sweating, but no difference in major adverse events was judged to be associated with corticosteroid use. ³⁵ In this study, 49.2% of patients in the corticosteroid group reported at least one minor adverse event at three weeks, compared to 23.9% in the placebo group, with insomnia being the most commonly reported. ³⁵

Theoretical concerns remain regarding corticosteroid administration, including risk of infection, avascular necrosis, or hyperglycemia. 36 Despite theoretical concerns, large meta-analyses analyzing randomized controlled trials demonstrated there is no difference in major adverse outcomes following corticosteroid administration, including rates of postoperative infection. 37, 38 In fact, a significant decrease in pulmonary complications was found in the corticosteroid group as compared to placebo, while no significant differences were found between groups in regard to avascular necrosis, significant gastrointestinal bleeding, psychiatric complications, or death by any cause. 38 The effects of corticosteroids on blood glucose level seem to be inconsistent, with some studies reporting no difference in blood glucose levels following corticosteroid administration, while others report a significant increase up to one day postoperatively.37 One study evaluated 98,390 patients that had received a single methylprednisolone taper pack over a 12 year period and found a low, but statistically significant, rate of osteonecrosis of .132% compared to 0.083% in controls, corresponding to a number needed to harm of 2041 patients.³⁹ In a survey completed by orthopaedic surgeons prescribing short-term oral corticosteroids to high school and college athletes, none reported any cases of osteonecrosis or infection following administration.40

As with all studies, a potential risk is a breach of confidentiality. Procedures for maintaining confidentiality are detailed below.

There is no current literature clearly establishing the role of methylprednisolone taper in patients with decreased ROM or delayed recovery following TKA. However, as described previously, corticosteroids have been shown to reduce pain and improve function in the immediate postoperative period following TKA, without an increase in adverse events. Therefore, we hypothesize that methylprednisolone taper at six weeks postoperatively in the appropriate patient cohort may improve ROM and recovery. However, because this is a double-blinded randomized controlled trial, there is approximately a 50% chance of being assigned to the placebo group. Furthermore, data from this study may help future patients who are experiencing delayed recovery in the postoperative period following TKA.

XVI. Procedures for maintaining Confidentiality:

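### Section VII gives no rule for combining its inclusion criteria: all-required is much narrower than the Purpose, and any-of lets NSAID allergy alone qualify a patient

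*Combined protocol and SAP*

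**What the plan says.** Section VII has eight bullets with no connecting word between them. Three apply naturally to everyone: primary TKA for osteoarthritis, adult age, and willingness to be randomized. Four describe slow recovery: "ROM <90° by 3 weeks postoperatively without improvement to >90° by 6 weeks"; "Requiring a 30-pill oxycodone refill"; "Thigh circumference discrepancy >2cm between legs from 3 to 6 weeks"; and a DVPRS score above 5 between weeks 3 and 6. The remaining bullet is "NSAID allergy", with no qualifier.

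Section III defines the target as patients with "decreased range of motion (ROM) or delayed recovery in the acute postoperative period". Section XII screens charts against the list at three weeks and approaches patients at the six-week visit "If these patients continue to meet inclusion criteria at six weeks postoperatively". It adds no rule for combining the bullets.

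The primary outcome in Section X is "Change in ROM from pre-treatment to 8 and 12 weeks post-operatively". Section IX gives the baseline data: "Age, sex, height, weight, BMI, ASA score, comorbidities, and smoking status will be collected". Section XII adds flexion, DVPRS and KSS at consent.

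**The concern.** An inclusion list defines the population only if the reader knows how its items combine. Here two screeners could follow the same page and enrol very different patients. Recruitment runs through four surgeons and several sites, so the rule cannot be left to one person's understanding.

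The NSAID allergy bullet makes the gap matter. The Background names pain, swelling and stiffness as contributors to delayed recovery. The DVPRS and refill bullets correspond to pain, the thigh bullet to swelling and the ROM bullet to stiffness. Allergy corresponds to none of them, and its role is not explained anywhere. At stake are a clear statement of whom the result applies to and, if patients without a recovery problem enter, some sensitivity of a trial whose only primary outcome is ROM.

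**Working it through.** **1. The two literal readings against the Purpose.** On either reading, the three general conditions have to apply to everyone; the list does not mark even that split.

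- *All required.* A patient needs ROM below 90° not recovered by week 6, an oxycodone refill, NSAID allergy, a thigh discrepancy and a DVPRS above 5, all together. Restricted ROM and allergy become mandatory. A patient with delayed recovery but adequate ROM is within the Purpose and cannot enter.
- *Any one of the five clinical bullets.* This fits the word *or* in the Purpose. But a patient whose only qualifying item is NSAID allergy can enter with normal motion, pain and swelling. The six-week recheck would not remove that patient, because the allergy is still present.

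**2. Time windows.** The ROM, thigh and DVPRS bullets each carry a window. The refill bullet carries none; one is only implied by the screening at three and six weeks.

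**3. The plan's power figure.** Inputs from Section XIII: difference 10°, SD 16.0°, alpha 0.05, 56 per arm. Two-sided testing is assumed, since the section does not say. The standardised difference is 10/16 = 0.625. A two-sample t-test needs 54.8, so 55 per arm, for 90% power. At 56 per arm power is 90.6%. The plan's figure is reproduced closely.

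**4. Illustration of dilution (assumptions, not document figures).** Let s be the allergy-only share, g their average gain from treatment, and 10° the average gain in everyone else. The mean difference is 10(1 − s) + g·s. With s = 0.10 (about 11 of 112), SD 16 and 56 per arm:

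| g | Mean difference | Power |
|---|---|---|
| 0° | 9.0° | 83.9% |
| 5° | 9.5° | 87.6% |
| 10° | 10.0° | 90.6% |

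A 10% share could arise, for example, from an allergy rate of 5% independent of recovery, with 30% of patients qualifying by other routes: 0.05 × 0.70 / (0.30 + 0.05 × 0.70) = 0.035/0.335 = 10.4%. The documents give neither rate.

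**5. Baseline adjustment.** With equal SD σ at both times and correlation r between them, the change score has variance 2σ²(1 − r). The baseline-adjusted outcome has residual variance σ²(1 − r²). The ratio is (1 + r)/2.

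| Assumed r | Ratio | Variance reduction |
|---|---|---|
| 0.3 | 0.65 | 35% |
| 0.5 | 0.75 | 25% |
| 0.7 | 0.85 | 15% |

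The document specifies no such adjustment. Flexion at consent is already recorded under Section XII.

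**The case against.** The strongest reply is that nobody would apply the list so literally. The title, Purpose, Hypothesis and Background all limit the trial to slow recovery, and the attending surgeon and study staff approach each patient in person. Section XII also speaks of flexion remaining below 90° when describing eligibility for MUA at week 8, which hints at restricted motion on entry. This stands as a reason to expect few allergy-only entrants. It does not supply a rule, and the MUA wording is not an entry criterion.

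A reader might infer that the all-required reading contradicts the Purpose. It does not: anyone meeting every bullet does have decreased ROM or delayed recovery. The reading selects a narrow part of the intended population.

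A reader might also infer that the trial is materially underpowered. The documents do not support that. The 10° in Section XIII is the change regarded as clinically important, not a forecast for any subgroup, and power to detect a true average difference of 10° does not depend on the mix. A loss appears only after assuming an allergy-only share, a smaller gain in those patients and a full 10° in all others, including pain-only or swelling-only entrants who may themselves have good flexion. The result also depends on taking 16° as the SD of the change. With equal SDs of 16° at both times, that corresponds to r = 0.5.

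Finally, it would be too strong to say that the enrolled mix could not be reported. Flexion, DVPRS and comorbidities are collected, and charts are used to identify patients. What is missing is an explicit field for allergy and for the qualifying sign.

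**Conclusion.** The point holds as a defect in the eligibility rule and should be corrected. No section says how the criteria combine, and neither literal reading delivers the population in the Purpose: one is much too narrow, and the other admits patients on an unexplained item unrelated to recovery. This conclusion needs no numerical assumption.

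The size of the consequence is uncertain. Under the stated assumptions, a 10% allergy-only share costs between 0 and about 7 percentage points of power (90.6% to 83.9% at worst). The share could be smaller or larger, since the documents give no allergy rate or enrolment mix. The figures show what could be lost and are not evidence that it will be.

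Adjusting for baseline flexion is a separate gain in precision, 15% to 35% less variance than unadjusted change for assumed r from 0.7 down to 0.3. It does not replace a clear entry rule.

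**What to change.** - Split Section VII into (a) conditions every patient must meet and (b) signs of delayed recovery. State how the signs in (b) combine and give the assessment window for each, including the oxycodone refill.
- The sponsor should reconcile the NSAID allergy bullet with the Purpose and state its role. This review does not say which criterion is right.
- Add two baseline fields to Section IX: NSAID allergy, and the sign or signs by which the patient qualified.
- Specify that the primary ROM change is analysed with adjustment for flexion recorded at consent.

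The cost is amendment wording, two data fields and one covariate that is already collected. If the sponsor decides that allergy is not a qualifying sign, any patients who would have entered on that ground alone are lost to recruitment.

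### The daily VAS pain score has no scheduled same-scale reading before the first capsule; this costs precision on a secondary outcome but does not bias it

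*Combined protocol and SAP*

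**What the plan says.** Section XI, item 1b, makes daily pain a secondary outcome: "Daily Visual Analogue Scale (VAS) pain score on days 1-6 of treatment". Section XII repeats the schedule and gives the channel: "VAS pain score will be collected daily on days 1-6 of the taper, via STREAMD". No VAS is listed before treatment or after day 6.

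The other pain measure follows a different schedule. Item 1a of section XI has "DVPRS and Knee Society Score (KSS) at pre-treatment, and 1 week, 3 weeks, 6 weeks, 12 weeks post-treatment", and section XII confirms that "PROMs collected at the time of consent will include DVPRS and KSS". Section VII also uses the DVPRS for eligibility: "Defense and Veterans Pain Rating Scale (DVPRS) > 5 between 3 and 6 weeks".

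On timing, section XII states "Day one is defined as day of consent" and says that the assigned capsules "will be administered at the conclusion of the follow-up appointment". Appendix 1 spreads the Day 1 capsules over four times of day. Neither place says when the Day 1 VAS is to be answered relative to the first of them.

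No analysis of the daily VAS is described: no change score, covariate, model or summary over the six days.

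**The concern.** Range of motion, DVPRS and KSS each have a stated pre-treatment value. The daily VAS does not, although it is the only outcome scheduled on every day of dosing. The first VAS falls on the day treatment starts. Because its order relative to the first capsules is open, it may be pre-dose in some patients and post-dose in others. It is then neither a clean baseline nor a clean on-treatment score.

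Two things follow. A change in VAS from before treatment cannot be formed. And unless the analysis adjusts for some other baseline pain score, stable differences in pain between patients stay in the error term of the daily comparison. A reading not taken before the first capsule cannot be recovered later, so the matter has to be settled before enrollment.

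**Working it through.** **The plan's own figure.** The only sample-size figure is for range of motion: 112 patients (56 per arm), difference 10°, SD 16.0°, alpha 0.05, power 90% (section XIII). By the two-sided normal approximation, n per arm = 2 × (1.960 + 1.282)² × 16² / 10² = 53.8, so 54. By the two-sample t-test it is 54.8, so 55 per arm (110 in all). Power at 56 per arm by the t-test is 90.6%. The figure reproduces closely, but it says nothing about pain. It is used below only to fix the number of evaluable patients.

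**Which pain readings exist.**

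| Time | VAS | DVPRS |
|---|---|---|
| Consent, before treatment | none listed | yes |
| Day 1 (consent day) | yes, order relative to first capsules not stated | none beyond consent |
| Days 2-6 | yes | none |
| 1, 3, 6 and 12 weeks post-treatment | none | yes |

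So a baseline pain score exists for each patient, but not on the scale used for the daily outcome.

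**Validity without a baseline.** In 20,000 simulated trials with no treatment effect, 56 per arm and a baseline-to-daily correlation of 0.6, a t-test on the daily score that ignored baseline rejected in 5.1% of trials at the nominal 5%. Omitting the baseline does not distort the comparison of arms.

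**Precision.** Let r be the correlation between baseline pain and a daily VAS. It is not in the documents; 0.3 to 0.7 is assumed.

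- Residual variance after adjustment, relative to none: 1 - r². The share removed is r².
- Equivalent unadjusted sample size: 112 / (1 - r²).
- Detectable difference at 80% power, in SD units: (1.960 + 0.842) × √(2/56) × √(1 - r²).

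| Analysis | Variance remaining | Variance removed | Equivalent unadjusted N | Detectable difference (SD) | Power for 0.5 SD |
|---|---|---|---|---|---|
| No baseline | 1.00 | 0% | 112 | 0.53 | 75% |
| Adjusted, r = 0.3 | 0.91 | 9% | 123 | 0.51 | 79% |
| Adjusted, r = 0.5 | 0.75 | 25% | 149 | 0.46 | 86% |
| Adjusted, r = 0.7 | 0.51 | 49% | 220 | 0.38 | 96% |

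At r = 0.7, 0.7² = 0.49 is removed and 0.51 remains. The rows apply to whichever baseline has that correlation, a pre-dose VAS or the consent DVPRS.

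**Change score.** Its relative variance is 2(1 - r), which is below 1 only if r exceeds 0.5. Power for 0.5 SD would be 61%, 75% and 93% at r = 0.3, 0.5 and 0.7. A pre-dose VAS is therefore better used as a covariate than subtracted.

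**What the missing VAS reading itself costs.** The table compares adjusting with not adjusting. The cost of having only a DVPRS baseline is the gap between two correlations, neither of which is given. As an illustration, suppose a pre-dose VAS correlated 0.6 with the daily score and the consent DVPRS 0.5. Residual variance would be 1 - 0.36 = 0.64 against 1 - 0.25 = 0.75, a further reduction of 1 - 0.64/0.75 = 15%.

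**The case against.** The strongest reply is that little is lost. A pre-treatment DVPRS is planned for every patient, and a covariate need not share the outcome's scale. The plan says of patients that "they will be randomized to one of two treatment groups", so the difference between arms needs no baseline to be valid. Chance imbalance in entry pain is ordinary random error, already covered by the standard error. No VAS change score is planned, so none is taken away. The item is secondary: the primary outcome is range of motion, and the hypothesis in section IV concerns two weeks after treatment starts.

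All of that stands, and it rules out several stronger readings:

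- A reader might infer that the early pain effect has no baseline at all, or is biased. The consent DVPRS and the randomization contradict both.
- A reader might take the 9% to 49% as the price of changing scale. It is the gain from adjusting rather than not adjusting, and the DVPRS can supply part of it.
- A reader might assume that entry pain varies widely because the DVPRS threshold is one alternative among several. Section VII does not say whether any or all of its items are required.
- A reader might think that moving from DVPRS to VAS and back distorts the result. Both arms use the same instrument on any given day. What is lost is only a single pain curve on one scale.

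The reply does not remove the point. Nothing commits the analysis to the DVPRS or any other covariate, the order of the Day 1 VAS and the first capsules is not fixed, and a same-scale baseline can be had only if it is scheduled.

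**Conclusion.** The point holds as a minor one on a secondary outcome. The daily VAS has no scheduled same-scale pre-treatment reading, and Day 1 may mix pre-dose and post-dose scores, so a VAS change from baseline cannot be computed. The comparison between arms remains unbiased. The loss is precision: 9% to 49% of residual variance if no baseline is used, and less if the consent DVPRS is used. These sizes rest on an assumed correlation of 0.3 to 0.7 and on 56 evaluable patients per arm, a number set for range of motion. The facts about the schedule come straight from the text and need no assumption.

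**What to change.** In sections XI (item 1b) and XII, schedule one VAS reading at the consent visit, before the first capsule. Add one analysis sentence, for example: the VAS on days 2-6 will be compared between arms in a repeated-measures linear model adjusted for the VAS taken before the first capsule; the Day 1 VAS will be described only. If no VAS reading is added, put the DVPRS taken at consent in its place as the covariate, which needs no new data.

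The cost is one extra pain rating per patient, through a channel already in use, and one sentence of analysis. Using the DVPRS instead of the VAS on days 1-6 would put all pain scores on one scale with the same number of messages, but would lose direct comparison with studies that report a VAS. It is optional.

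### No systematic collection of common steroid side effects is described, and the three named safety outcomes can say little about tolerability in 136 patients

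*Combined protocol and SAP*

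**What the plan says.** Section XI.3 is the only safety outcome: "Adverse outcomes including infection, avascular necrosis, and 90-day readmission rates". It gives no definition, grading or method of ascertainment. The time frame of 90 days attaches to readmission.

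Section XV attributes most of the potential risk to the medication and lists side effects by organ system. It cites a randomised trial of a 15-day oral prednisone taper for lumbar radiculopathy in which "49.2% of patients in the corticosteroid group reported at least one minor adverse event at three weeks", against 23.9% on placebo, with insomnia reported most often. The same paragraph says that risk rises with dose and duration, and classes the present taper as low-dose and short. For osteonecrosis after a single taper pack, Section XV cites a "statistically significant, rate of osteonecrosis of .132% compared to 0.083% in controls", "corresponding to a number needed to harm of 2041 patients".

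Section XII is specific about patient contact. "Daily text messages will include reminders with the required number of pills" for that day of the taper. The same text service collects a daily VAS pain score on days 1 to 6 and DVPRS at 1, 3, 6 and 12 weeks after treatment; KSS is collected at those weeks through another system. Patients who cannot use these services are surveyed by phone. ROM is extracted from charts. No contact is described that asks about side effects.

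**The concern.** The protocol puts drug side effects at the front of its risk discussion, yet its outcome list and contact schedule describe no systematic way to record the common ones. What remains is one event that the protocol's own figures show to be very rare, and two whose frequency it does not state.

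A finding of no difference in the named outcomes would then be easy to read as good tolerability when it carries almost no information on that. A gain in ROM could not be weighed against insomnia, nervousness, indigestion and similar effects, because nobody would have asked both arms the same question at the same time.

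**Working it through.** **Inputs.** From Section XIII: SD 16.0°, difference 10°, alpha 0.05, 56 evaluable and 68 recruited per arm. From Section XV: osteonecrosis 0.132% versus 0.083%; any minor event 49.2% versus 23.9%. Assumed, because the documents give no figures: control rates of 1% to 10% for infection or readmission, doubled on steroid.

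**The plan's own figures.** Section XIII states: "At an alpha of 0.05, 112 patients (56 per arm) will provide 90% power to detect a 10° change". A two-sided comparison of means needs n = 2(1.960 + 1.282)² × 16² / 10² = 53.8, so 54 per arm; the t-test version gives 55. At 56 per arm power is 91.1% (normal) or 90.6% (t), so the statement is sound. "Assuming a 20% dropout, 136 patients (68 per arm) will be recruited" matches 56 × 1.2 = 67.2, rounded up to 68. The number needed to harm also reproduces: 1 / (0.00132 − 0.00083) = 2041. No power is stated for any safety outcome.

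**Avascular necrosis at the cited rates, 68 per arm.**
- Expected cases: 68 × 0.00132 = 0.09 on steroid and 68 × 0.00083 = 0.06 on placebo.
- Chance of no case in either arm: (1 − 0.00132)^68 × (1 − 0.00083)^68 = 86%.
- One-sided 95% upper bound if 0 of 68 have the event: 1 − 0.05^(1/68) = 4.3%, about 33 times the cited 0.132%.
- Patients needed for 80% power at these rates: about 70,200 per arm.

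**Power formula for two proportions.** Power = Φ[(|p1 − p0| − 1.96·s0) / s1], with s0 = √(2·p̄(1 − p̄)/n), s1 = √((p1(1 − p1) + p0(1 − p0))/n) and p̄ = (p1 + p0)/2.

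**Infection and readmission, 68 per arm, steroid rate double the control rate.**

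| Assumed control rate | Power to detect a doubling |
|---|---|
| 1% | 7% |
| 2% | 10% |
| 5% | 20% |
| 8% | 30% |
| 10% | 37% |

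Fisher's exact test is lower throughout (0.1% to 29%). With a 5% control rate, the steroid rate would have to reach about 21% for 80% power.

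**Any minor event, placebo rate 23.9%.** At the cited rates with n = 68: p̄ = 0.3655, s0 = 0.0826, s1 = 0.0797, so power = Φ[(0.253 − 0.1619) / 0.0797] = Φ(1.14) = 87%. Half the cited excess is 23.9% + 12.65 points = 36.55%.

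| Steroid rate | Power, 56 per arm | Power, 68 per arm | 95% CI half-width, 68 per arm (1.96·s1) |
|---|---|---|---|
| 49.2% | 80% | 87% | ±15.6 points |
| 45% | 66% | 74% | ±15.6 points |
| 40% | 45% | 52% | ±15.4 points |
| 36.55% | 31% | 36% | ±15.3 points |

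**Effect of a joint-pain item.** The cited trial counted joint pain among its minor events. Suppose, as an assumption, that a fraction q of these patients report joint pain whatever their arm, independently of the other events. With q = 50%, the composite becomes 1 − 0.508 × 0.5 = 74.6% versus 1 − 0.761 × 0.5 = 61.95%, and power at 68 per arm falls from 87% to 35%. With q = 30% it is 55%; with q = 80% it is 14%.

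**The case against.** The strongest reply is that 49.2% versus 23.9% describes another drug, a 15-day course and another condition, while this taper lasts six days and the protocol itself says that risk falls with dose and duration. That stands. A reader might infer that the protocol expects these rates here, or that the trial is amply powered for side effects. The documents support neither, and 87% is a best case.

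A reader might also infer that all three named outcomes are too rare to study. The documents show this only for avascular necrosis. For infection and readmission the claim is the weaker one of low power over an assumed range.

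Nor do the documents show that side effects will go unrecorded. The word including in XI.3 leaves the list open, charts are already read for ROM, and the consent pages are not in the text, so what patients are told to report cannot be judged. What can be said is that no systematic collection is described. Spontaneous reports and chart notes do not give a comparable numerator in each arm.

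Finally, the stated purpose is efficacy, and serious harms deserve recording even when the trial cannot compare them. Both are fair, and neither argues against adding a common outcome. A milder taper is itself a reason to measure: the authors believe theirs is the first study of such a taper in this postoperative window, so a small difference with its interval would be useful evidence.

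**Conclusion.** The point holds as a gap in measurement. The protocol names three safety outcomes that can show only large differences in 136 patients, and describes no systematic capture of the common effects to which its risk section gives prominence. A null result on the named outcomes would say little about tolerability.

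The avascular necrosis figures rest on the protocol's cited rates. The infection and readmission figures rest on assumed control rates and a doubling. The minor-event figures assume a placebo rate of 23.9% and complete data at 68 per arm. Because power for a minor-event difference runs from 87% down to 36% over plausible steroid rates, the outcome should be estimated with its interval, not presented as a powered test. It is worth correcting, but it does not affect the primary analysis.

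**What to change.** Add to XI.3 an outcome of any patient-reported minor side effect by 3 weeks. In Section XII, specify:

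- a short fixed yes/no list: insomnia, nervousness, increased appetite, indigestion, headache, sweating. Omit joint pain, which overlaps with the knee condition and would dilute the composite;
- delivery by the existing text service, or the existing phone fallback, on day 6 and at 3 weeks, sent after that day's pain score so that it cannot colour the score;
- reporting of each item and of the composite by arm, as a difference in proportions with a 95% confidence interval. Keep infection, avascular necrosis and readmission as counts by arm, with intervals and no claim of equivalence.

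The cost is two short messages per patient on a system already in use, with no new visit and no change to treatment. The downside is that the prompts may lead some patients to guess their arm, which could affect later patient-reported outcomes.
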